10.4 Causality Assessment

The following “binary” decision choice will be used by the Investigator to describe the causality assessment:

- Reasonable possibility of a relatedness
- No reasonable possibility of relatedness

The expression “reasonable possibility of relatedness” is meant to convey, in general, that there are facts (evidence) or arguments meant to suggest a causal relationship.

The Investigator will be asked to consider the following before reaching a decision on causality assessment:

- Time relationship between study drug intake and event’s onset;
- De-challenge (did the event abate after stopping drug?);
- Re-challenge (did the event reappear after reintroduction?);
- Medical history;
- Study treatment(s);
- Mechanism of action of the study drug;
- Class effects;
- Other treatments-concomitant or previous;
- Withdrawal of study treatment(s);
- Lack of efficacy/worsening of existing condition;
- Erroneous treatment with study medication (or concomitant);
- Protocol related process.

10.5 Action taken with the study drug due to an AE

- Dose not changed
- Drug permanently withdrawn
- Drug temporarily interrupted
- Unknown
- Not applicable

10.6 Other actions taken

- Specific therapy/Medication
- Concomitant Procedure
- N/A

10.7 Outcome

Each Adverse Event must be rated by choosing among:

Clinical Study Code No.: CLI-06563AA1-02	Version No.: 6.0
IND No.: 131,339	Date: 18 March 2021

- Recovered/resolved
- Recovering/resolving
- Not recovered/not resolved
- Recovered with sequelae/resolved with sequelae
- Fatal
- Unknown

10.8 Recording Adverse Events

All Adverse Events occurring during the course of the study must be documented in the Adverse Event page of the electronic Case Report Form (eCRF). Moreover, if the Adverse Event is serious, the Serious Adverse Event Form must also be completed.

It is responsibility of the Investigator to collect all adverse events (both serious and non-serious). Signs of NOWS (the condition under study) are efficacy endpoints in this study. Since detailed information on these events will be collected on the relevant page (refer to [APPENDIX 4 – Finnegan Neonatal Abstinence Scoring Tool \(FNAST\)](#)), these events therefore do not require to be reported as AEs unless their occurrence, severity or unresponsiveness to treatment (both study arms) is considered by the investigator unusual or abnormal or suggest another clinical diagnosis or pathology.

Additionally, those events should be reported as SAEs if they fulfill the definition of an SAE as in [section 10.1](#)

All AEs, regardless of seriousness, severity or presumed causality must be recorded in the subject's medical records and in the CRF. AEs that occur in subjects who have screen failed and are not entered into the CRF will be captured on the AE Reporting Log in the Investigator Site File. All SAEs occurring in subjects who have screen failed will be reported from informed consent and recorded in eCRF.

The investigator should carefully check inclusion and exclusion criteria because some of these morbidities may not allow the neonate to be randomized.

Clinically significant abnormalities detected at Screening visit not due to a pre-existing condition or clinically significant changes at the following visits in the medical opinion of the investigator must be reported as adverse events in the eCRF, taking into consideration the above assessment.

A diagnosis, if known, or clinical signs and symptoms if diagnosis is unknown, rather than the clinically significant abnormal laboratory finding, should be reported on AE [eCRF](#) page. If no diagnosis is known and clinical signs and symptoms are not present, then the abnormal finding should be recorded.

For pharmacovigilance purposes, all SAEs should be followed-up in order to elucidate as completely and practically as possible their nature and/or causality until resolution of all queries, clinical recovery is complete, laboratory results have returned to normal, stable condition is reached or until the subject is lost to follow-up. Follow-up may therefore continue after the subject has left the study. In this case, the follow-up will continue with no timelines for related SAEs, while for unrelated SAEs the type and extent of follow-up undertaken will be determined for each individual case and will depend upon the nature (e.g. events with poor prognosis or which do not resolve), severity and medical significance of the event.

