1. INTRODUCTION

1.1 Background information

Neonatal opioid withdrawal syndrome (NOWS) is a subset of Neonatal abstinence syndrome (NAS) and refers to neonatal withdrawal from opioid drugs and can occur in the presence of other drug withdrawal syndromes. In the United States, neonatal withdrawal following in-utero opioid exposure is typically the result of prolonged maternal use and/or abuse of illicit or prescribed opioids during pregnancy. Birth leads to the abrupt cessation of fetal substance exposure and can precipitate acute withdrawal symptoms that can result in severe health complications with prolonged recovery and longer hospitalization. Withdrawal can be both severe and intense, with an estimated 60% to 80% of exposed neonates requiring pharmacological intervention to control symptoms [1][2].

While the signs and symptoms of NOWS are similar to those experienced by adults undergoing acute opiate withdrawal, they present a higher risk to the neonate due to the babies' dependence on others for all aspects of well-being.

NOWS presenting signs include central nervous system hyperirritability (tremors, jitteriness, irritability, hyperactive muscle reflexes, and excessive high-pitched cry), autonomic nervous system deregulation and instability (tachypnea, nasal flaring, hyperphagia, temperature instability, insomnia, sweating, mottled skin, yawning, and sneezing), and gastrointestinal symptoms (diarrhea, vomiting, and poor feeding) [3][4][5]. Seizures are generally rare, although they have been reported occurring in 2% to 11% of neonate cases in the early stage of severe opioid withdrawal [6][7], especially if medical treatment has been delayed. A recent large observational cohort study of Medicaid babies in 46 US States reported an incidence of seizures was 2.7% among the 1705 observed cases of NAS [8]. Neonates with NOWS can also experience weight loss or failure to thrive, which often results from a combination of poor feeding, vomiting, nausea, and diarrhea [4][5]. If left untreated, some cases of NOWS may even lead to death [5]. Some of the less severe signs and symptoms of opiate withdrawal may persist for several months [3].

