2. STUDY OBJECTIVES

2.1 Primary Objective(s)

- To assess the efficacy of CHF6563 in babies with NOWS
- To assess the safety and tolerability of CHF6563 in babies with NOWS

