9. SAFETY ASSESSMENTS

During administration of sublingual CHF6563 or oral morphine:

- Number and percentage of babies with peri-dosing adverse events (AEs) (i.e., mouth irritation or inflammation, apnoea, desaturation, brady/tachycardia, cough, immediate swallowing of sublingual drug, regurgitation, vomiting occurring after administration)

During the study

From the randomization to the end of the treatment the following information will be collected and presented using summary statistics:

- Adverse events and adverse drug reactions (ADRs).
- Liver enzymes analysis-function testing (AST, ALT,) will be performed on 3 occasions: after the first dose, at stabilization and 48 hours (± 4 h) after the last treatment dose.
- Vital signs: heart rate (HR), respiratory rate (RR), peripheral oxygen saturation (SpO₂), body temperature (BT) will be monitored, and data collected during the escalation and stabilization phases.
- Body Weight and head circumference
- Hematology and blood chemistry: full blood count (FBC), urea, creatinine and electrolytes (sodium, potassium, magnesium calcium, phosphorus), glucose, C-reactive protein if collected before randomization according to site clinical practice.
- Blood pressure (SBP, MBP, DBP) will be monitored according to individual site clinical practice

End of the treatment period

After 48 hours (± 4 h) from the last dose the following will be recorded and presented using summary statistics:

- Vital signs: heart rate (HR), respiratory rate (RR), peripheral oxygen saturation (SpO₂), body temperature (BT). Blood pressure (SBP. MBP. DBP) if collected according to site clinical practice
- Neurological and behavioral assessment
- Body weight, length and head circumference
- All the Adverse Events, and adverse drug reactions, and concomitant medications as well as changes in those already reported.

End of 6 week Follow up

- Signs of / escalation of withdrawal
- All the Adverse Events, and adverse drug reactions, and concomitant medications as well as changes in those already reported.

Follow up to 18 months

- Health status (general medical history and physical examination, including growth parameters, medical illness, developmental issues, medications and hospital admission)
- Environmental / social factors (foster care, domestic violence exposure, substance use / treatment)
- Cognitive and behavioral development (Bayley Scales of Infant Development - all 5 domains)

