12.3.7 Safety variables

Adverse Events

Safety analysis will be based on Safety population. All adverse events starting on or after the time of first study drug intake will be classified as treatment emergent adverse event (TEAE). Any adverse events started after the informed consent signature and before the time of first study drug intake will be classified as pre-treatment adverse events.

The number of babies who experienced at least one TEAE, drug-related TEAE, serious TEAE, serious related TEAE, TEAE leading to study discontinuation, TEAE leading to death, and peri-dosing TEAEs will be summarized by treatment arm. Summaries will be presented overall (number and percentage of babies having at least one event, total number of events) and by system organ class and preferred term (number and percentage of babies having at least one occurrence of that event).

All adverse events will be listed.

Pre-treatment adverse event will be listed only.

The peri-dosing AEs are defined as adverse events occurring during or shortly after administration of study treatment, i.e. within 10 minutes from the start of study drug administration.

Vital signs

Vital signs will be summarized at each planned time point by means of descriptive statistics. At each timepoint when vital signs are collected, mean, min, max and standard deviation of the observed values and change from baseline will be presented, in addition to being listed.

Laboratory data

Sites will use local labs to obtain liver enzymes analysis-function testing. When consistent with site clinical practice, sites will use local labs to collect hematology and blood chemistry. The laboratory values and the change from baseline for continuous laboratory parameters will be summarized by descriptive statistics at each planned time point. All laboratory data will be listed with abnormal values flagged.

Head circumference (and percentile) and body weight (and percentile)

Head circumference (and percentile) and body weight (and percentile) and their corresponding changes from baseline will be summarized using descriptive statistics at each planned time point.

Additional Safety Variables

The following parameters collected only at the end of the treatment period will be listed only:

- Neurological and behavioral assessment

Analysis of safety variables collected at the 18-month follow up visit will be described in the SAP.

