3. SAFETY ANALYSES

3.1 ADVERSE EVENTS

3.1.1 *Available data*

Adverse events (AEs) are coded into system organ classes and preferred terms using the medical dictionary for regulatory activities (MedDRA). For each AE, start and stop date(time)s are collected as well as severity, a seriousness flag, treatment-relatedness, action taken towards the study drug and outcome.

3.1.2 *Derivation rules*

Pre-treatment AEs are defined as AEs starting between date(time) of informed consent and the date(time) of first study drug administration – 1 minute.

Treatment-emergent adverse events (TEAE) are defined as AEs starting on or after first administration of any study drug.

Peri-dosing TEAEs are defined as AEs included in the list below occurring during or shortly after study drug administration, i.e. within 10 minutes from the start of study drug administration:

- mouth irritation or inflammation,
- apnea, desaturation,
- brady/tachycardia,
- cough,
- immediate swallowing of sublingual drug,
- regurgitation,
- vomiting occurring after administration.

Note: the list of preferred terms to be selected as peri-dosing TEAEs will be finalized prior to database lock and documented in the DRR. For AEs start dates with missing time information where no other database information indicates that AE started outside the peri-dosing interval, the worst-case principle will be applied and these AEs will be considered as peri-dosing.

Post-treatment AEs are defined as AEs starting on or after the start of the follow-up phase.

Based on their start date(time), AEs will be allocated to the phase during which they started. Phases are defined in section 5.2.1. In case the AE start date(time) is incomplete or missing and the AE could consequently be allocated to more than one phase, a worst-case allocation will be done as detailed below:

- Treatment phase vs. non-treatment phase: AE will be allocated to the treatment phase unless the available parts of the AE stop date(time) provide evidence for allocating to the non-treatment phase.

A fatal AE is defined as an AE with outcome 'fatal'.

An AE for which the study drug was discontinued is defined as an AE with action taken 'drug withdrawn'.

AE onset and duration will be calculated as follows when start and stop dates are fully known:

- AE onset day (vs. first administration) =
 - AE start date < date of first administration: AE start date – date of first administration

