3.4 ESCALATION OF OPIOID WITHDRAWAL

3.4.1 Available data

The following signs of escalation of opioid withdrawal are collected:

- Crying - excessive / continuous
- Persistent inability to sleep
- Tremors and jerks
- Sweating
- Fever
- Mottling
- Nasal stuffiness
- Sneezing
- Poor Feeding
- Regurgitation
- Projectile vomiting
- Loose stools
- Watery stools

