4.6 EXPOSURE TO STUDY DRUG

4.6.1 *Available data*

For each study drug administration, the dates (time), the prescribed dose, the actual volume administered, rescue dose flag and issues occurred during dosing will be recorded.

4.6.2 *Presentation of results*

All exposure data will be listed.

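### Protocol 10.8 exempts NOWS signs from AE reporting with no peri-dosing exception, so the peri-dosing count can miss post-dose vomiting and possibly regurgitation

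*Protocol*

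**What the plan says.** **The objective and the measure.** Protocol 2.1 makes it a primary objective "To assess the safety and tolerability of CHF6563 in babies with NOWS". The first safety variable in Protocol section 9 is the number and percentage of babies with peri-dosing AEs. Its list has eight event types: mouth irritation or inflammation, apnea, desaturation, brady/tachycardia, cough and, in the protocol's words, "immediate swallowing of sublingual drug, regurgitation, vomiting occurring after administration".

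**How it is derived.** Protocol 12.3.7 sets the window: "The peri-dosing AEs are defined as adverse events occurring during or shortly after administration of study treatment, i.e. within 10 minutes" from the start of administration. SAP 3.1.2 adds the list: "Peri-dosing TEAEs are defined as AEs included in the list below occurring during or shortly after study drug administration". SAP 3.1.3 keeps peri-dosing TEAEs and peri-dosing ADRs as rows of the one AE summary table (14.3.1.1).

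**What must be reported.** Protocol 10.8 sends signs of NOWS to the FNAST page and says that "these events therefore do not require to be reported as AEs unless their occurrence, severity or unresponsiveness to treatment" is considered unusual or abnormal by the investigator, or suggests another diagnosis. Events that meet the SAE definition are still reported. The section does not mention the peri-dosing list.

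**What counts as a withdrawal sign.** Protocol 1.1 lists "gastrointestinal symptoms (diarrhea, vomiting, and poor feeding" among the presenting signs. SAP 3.4.1, on escalation of opioid withdrawal, lists regurgitation and "Projectile vomiting".

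**What else is collected.** For each administration, SAP 4.6.1 says that "issues occurred during dosing will be recorded". SAP 4.6.2 provides only for listing the exposure data.

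**The concern.** The same event, a baby vomiting minutes after a dose, falls under two rules. As a peri-dosing event it belongs in a named safety variable. As a sign of NOWS it need not be entered as an AE, and without an AE record it cannot enter that variable. The documents do not say which rule prevails, so the choice falls to the investigator and can differ between sites.

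The event is foreseeable: Protocol 6.2.2.1 and 6.2.2.2 both give instructions for a baby who spits or vomits soon after a dose. For a new sublingual liquid, this is information about how well dosing is tolerated. A low number, or a zero, in the peri-dosing row could reflect the recording rule rather than good tolerability.

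**Working it through.** No figure in the plan is at issue, so the check is mainly a comparison of the sections.

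1. **Which listed events overlap with NOWS signs.**
   - Vomiting overlaps clearly, because Protocol 1.1 names it.
   - Regurgitation overlaps on weaker ground. Only SAP 3.4.1 names it, and both schedules of assessments tick escalation of withdrawal signs only in the follow-up column, after dosing has ended. The item list of the FNAST form (Protocol Appendix 4) could not be checked, and that is not held against the plan.
   - The other six types appear neither in Protocol 1.1 nor in SAP 3.4.1.
   - So one of eight types is clearly affected, one possibly, and six are not shown to be.

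2. **Two permitted paths for a vomit within 10 minutes of a dose.** If it is entered as an AE, it is counted. If it is treated as a NOWS sign under 10.8, it goes to FNAST only and is not counted. Both are consistent with the text.

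3. **Whether another source closes the gap.**
   - FNAST is scored every 4 hours (± 1 hour). A nominal interval of 4 × 60 = 240 minutes, not tied to dose time, cannot place an event in a 10-minute window.
   - SAP 3.1.2 has a worst-case rule that treats listed AEs with a missing start time as peri-dosing. It applies only to events already entered as AEs.
   - The dosing-issue field sits with the dose record, but no rule carries its contents into the peri-dosing count.

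4. **Direction.** The exemption can only lower the count. The worst-case rule can raise it for AEs without a time, so the net error in the row is not fixed in sign. At baby level, an omitted vomit matters only if no other listed event was recorded for that baby. The number of events, also shown in the table, falls in any case.

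5. **Size.** Let p be the true share of babies with post-dose vomiting or regurgitation, and f the share of those babies whose events all go unreported. The observed share is p × (1 − f). The documents give neither value. For illustration only, take the 38 CHF6563 babies planned:
   - p = 10%, f = 50%: 38 × 0.10 = 3.8 babies become 38 × 0.10 × 0.5 = 1.9.
   - p = 20%, f = 50%: 38 × 0.20 = 7.6 become 38 × 0.20 × 0.5 = 3.8.
   - p = 20%, f = 25%: 7.6 become 38 × 0.20 × 0.75 = 5.7.

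6. **At the actual size.** SAP 6.1 reports 7 randomized. If all seven were dosed, one omitted baby is 1/7 = 14.3 percentage points overall. The arm split is not stated. If it were 5:2, one baby would be 1/5 = 20 points in the larger arm or 1/2 = 50 in the smaller.

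**The case against.** The strongest reply is that nothing forbids reporting. Section 10.8 makes the investigator responsible for collecting all adverse events, and its exemption says only that reporting is not required. Section 9 and SAP 3.1.2 name these events as peri-dosing AEs, and a reader may fairly hold that the specific list governs. Section 10.4 tells investigators to weigh the time between drug intake and onset. In addition, the trial stopped at seven babies, and SAP 6.1 says the objectives are not evaluable. Exposure data, FNAST scores and TEAEs are all listed by subject, so cases can be cross-checked by hand.

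Much of this stands. A reader might infer that the count will be too low; the documents support only that it can be. A new protocol sentence cannot change the data of babies already treated. But no text says the peri-dosing list overrides 10.8, and listings do not correct the row that the table will show.

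A reader might also infer that functional unblinding makes the loss depend on arm for CHF6563. The documents do not support this. Protocol sections 3 and 7.1.6 place it after the last scheduled CHF6563 dose, so it cannot affect how events after CHF6563 doses are attributed. At most it could touch later doses in the morphine arm.

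**Conclusion.** The conflict is in the text and is not resolved elsewhere. By following 10.8, a site can leave post-dose vomiting, and possibly regurgitation, out of a peri-dosing count that names both. The count can therefore be too low and inconsistent between sites. The amount cannot be estimated from the documents; the figures for p, f and the arm split are assumptions that show scale only.

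The reach is limited: one listed event type clearly, a second possibly, in one measure under a primary objective. After early termination, what is left is the peri-dosing rows of table 14.3.1.1. With so few babies, a single omission would visibly change them.

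**What to change.** **For the analysis of the seven randomized babies (SAP 3.1.2).** The SAP already finalizes the peri-dosing term list before database lock and documents it in the data review report. At that step, compare the dosing-issue field with the AE records for every treated baby. Listed events found there within 10 minutes of dosing should either be counted in the peri-dosing row of table 14.3.1.1 or be shown in an added row. The report should say which was done and how an issue without a recorded time was handled. This can recover only what sites wrote in that field.

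**For any further use of the protocol (section 10.8).** Add that an event on the peri-dosing list starting within 10 minutes of a study drug administration is always recorded as an AE with its start time, even if it is also a sign of NOWS.

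**Cost.** One reconciliation check for at most seven babies, one protocol sentence and a site instruction. The downside is a few more mild AE entries and possibly a higher reported peri-dosing rate. Both changes concern recording and counting, not clinical management.

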10.10 Reporting Serious Adverse Events to Regulatory Authorities/Ethics Committees/IRB

The Sponsor or [REDACTED] will report adverse events to the regulatory authorities in compliance with the timelines and standards of reporting according to local regulations (Guidance for industry and Investigators-Safety Reporting Requirements for INDs and BA/BE studies, December 2012). All suspected unexpected serious adverse reactions (SUSARs), which occur with the investigational medicinal product or marketed active comparator, within or outside the concerned clinical trial, will be reported by the Sponsor or [REDACTED] to regulatory authorities, as required, as well as to the Investigators and Central IRB, if applicable, by MedWatch/CIOMS form. The Investigator (or Sponsor/CRO where required) must inform the IRB per Sponsor instruction upon receipt of the SUSAR notification. An IND and/or NDA Safety Report will be submitted to regulatory authorities unblinded. Participating Investigators and IRB will receive a blinded IND Safety Report, unless otherwise specified. Regarding regulations in force for Pharmacovigilance, the Investigator must fulfill his/her obligation according to the law in force in his country.

